1.4 Development of Protocol

Consistent with practice-based research principles, the study protocol was developed utilizing input from multiple stakeholders organized into a Community Advisory Committee and a Scientific Advisory Committee as well as key feedback from practice-based research network (PBRN) directors. During the development of the study protocol, study procedures including enrollment and measuring of outcomes were piloted in a “model recruitment” study designed to mimic the procedures for the main trial and informed the procedures and outcomes described in this protocol.

1.5 Potential Risks and Benefits

1.5.1 Potential Risks

The emollients used in our current proposed study will be used in a similar fashion to how they are being used currently by the general public with only slight changes that should not change the safety profile of the emollients. Data from two published studies and our unpublished data reveal over 70% of parents are already using moisturizers on a daily basis on their infants.^{34,35} These data reveal parents primarily use watery lotions. Our hypothesis is that a basic moisturizer with higher lipid content than a typical lotion will reduce the risk of developing atopic dermatitis by providing better barrier repair than water-based lotions. We also hypothesize that more frequent use of a thicker emollient (i.e. daily) will lead to enhanced protection of the skin barrier than current skin care practices and thus reduce the probability of developing AD.

The daily use of moisturizers in infants in our proposed study will likely not pose an increased risk beyond current standard usage. The main risk of the emollient would either be the development of an irritant contact dermatitis or rarely an allergic contact dermatitis to an emollient component. Theoretically, occlusive moisturizers could increase the risk of a skin infection, however this has not been seen in previous clinical studies of emollients in neonates. Moisturizer marketing campaigns currently promote the daily use of moisturizers in infants. Parents will have a choice of multiple legally marketed moisturizers for this study that are all freely available over-the-counter.

Parents in the intervention arm will select an emollient from the approved moisturizers list to use on their baby over the course of the study. These emollients do not pose any additional known risk to newborns or infants beyond current usage patterns in the community.

There is a risk of loss of confidentiality. The study team will take precautions to protect the confidentiality of participant information.

1.5.2 *Potential Benefits*

It is not known if there are benefits to using the preferred emollient for infants not at risk of developing AD (i.e. there is no family history of AD or allergies). Some studies show infants at high-risk for developing AD may benefit from emollient therapy, but these studies were small and need confirmation. While participation in this study may not provide direct benefits to participants, participation may help to understand how to prevent AD in infants.

2 STUDY OBJECTIVES

2.1 Study Objectives

2.1.1 Primary Objective

To assess the effectiveness of daily emollient therapy beginning in the first 2 months of life in reducing the cumulative incidence of AD at 24 months of age in a community-based setting.

2.1.2 Secondary Objectives

To determine whether an atopic family history and key early life exposures modify the effect of emollient therapy on atopic dermatitis.

To assess the effectiveness of emollient therapy on the development of reported allergic comorbidity symptoms such as food allergy and wheeze episodes.

2.2 Study Outcome Measures

2.2.1 Primary Outcome

The primary outcome will be an AD diagnosis made by the infant's primary healthcare provider by 27 months of age (cumulative incidence). A diagnosis will be recorded in the health record for each infant and these data will be extracted by PBRN research coordinators. Diagnosis guidelines and documentation will be introduced at an initial training session and provider compliance with this protocol will be monitored and reinforced by PBRN research coordinators. Any diagnosis of AD made by the trained provider during the first 27 months of life will be considered as having developed AD (i.e., cumulative incidence). Clinicians will be trained to use the American Academy of Dermatology (AAD) Consensus Criteria for diagnosing pediatric AD.³⁷ These criteria are a distillation of the original Hanifin-Rajka criteria with minor enhancements made by pediatric dermatologists to facilitate diagnosis in the very young. The recently-published AAD guidelines of care for AD recommend these criteria for the diagnosis of AD in the clinical setting.³⁸ The statistical analysis plan contains the full set of primary and secondary outcomes.

Table 1: AAD Consensus Criteria for diagnosing pediatric AD.

| ESSENTIAL FEATURES |
|---|
| Must be present: |
| -Pruritus |
| -Eczema (acute, subacute, chronic) |
| -Typical morphology and age-specific patterns* |
| -Chronic or relapsing history |
| *Patterns include: |
| 1. Facial, neck, and extensor involvement in infants and children |
| 2. Current or previous flexural lesions in any age group |
| 3. Sparing of the groin and axillary regions |
| IMPORTANT FEATURES |
| Seen in most cases, adding support to the diagnosis: |
| -Early age of onset |
| -Atopy-personal and/or family history |
| -Immunoglobulin E reactivity |
| -Xerosis |

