4.3 Participant Exclusion Criteria

A dyad who meets any of the following criteria will be excluded from participation in this study:

- Infant born at less than 25 weeks gestational age
- Infant has established eczema as diagnosed by the primary healthcare provider at clinic site of enrollment per parent report
- Infant has known adverse reaction to petrolatum-based emollients
- Infant has an immunodeficiency genetic syndrome such as Wiskott-Aldrich Syndrome or Severe Combined Immunodeficiency Syndrome
- Infant has extremely low birthweight (less than 1000g or 2.2 lbs [2 pounds 3 ounces] at birth)
- Infant has a sibling enrolled in the study
- Parent is unwilling or unable to comply with study procedures

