4.6 Strategies for Recruitment and Retention

Regional clinics will utilize clinic workflows to identify eligible dyads as they present for scheduled well child visits or when mothers present for scheduled prenatal or postpartum visits. The typical structure will place a tablet computer in the waiting room, recruitment kiosk or exam room to initiate study procedures. Rack cards or recruitment postcards will be offered to families to review after the clinic visit or sent via mail or patient portal. Recruitment flyers will be placed in waiting rooms and exam rooms with enrollment URL and QR code. Front and back office clinical staff will direct parents to the tablet or recruitment materials to initiate screening and enrollment. Patient-focused recruitment videos will be made available to clinics for use in introducing the study to dyads.

Each PBRN will assign a research coordinator to support participant recruitment efforts at regional clinics. Research coordinators will meet regularly with clinic staff, either in person or over the phone, to keep clinic staff engaged in the study and help clinics meet their enrollment milestones. Research coordinators will also support clinics who encounter challenges with meeting the recruitment goal of two dyads per month through conducting small tests of workflow changes and clinical observations to identify opportunities for recruitment.

During approximately 24 months of study participation, parents will receive periodic study communications in multiple formats. Dyads will receive compensation (Table 2) to incentivize completion of questionnaires and to enhance participant retention. Dyads

randomized to the intervention group will receive 24 months' worth of emollient over the course of the study.

Table 2: Schedule of compensation

| Infant Age | Compensation for Completion of: | Compensation Amount |
|---------------------------------|---------------------------------|---------------------|
| 0 to 2 months | Enrollment Questionnaire | \$35 |
| 12 Months | 12 Month Questionnaire | \$50 |
| 24 Months | 24 Month Questionnaire | \$50 |
| Total Study Compensation | | \$135 |

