2.3. Sample Size and Recruitment Duration

1,250 parent/infant dyads (625 per arm) will be enrolled from 25 community-based family medicine and pediatric practices in four states (Oregon, Colorado, Wisconsin, and North Carolina). All parents/legal guardians, including males and females 18 years of age and older who meet inclusion/exclusion criteria are eligible for study participation. Recruitment is expected to take place over the course of 31 months; the time from start of recruitment until final two-year follow-up on all subjects is five years.

Power for Aim 1. For the purpose of the primary analysis, we include a sufficient number of babies in a 1:1 ratio for the two study arms to provide an overall type I error rate of 0.05 and 80% power to detect a 30% relative reduction in cumulative incidence of AD by two years of age (RR=0.7). In our planning grant, we determined the baseline cumulative incidence of AD in this age group and target clinics at 24%, which is consistent with recent population-based 2-year prevalence in the U.K.¹. Because our trials in high-risk populations of daily vs no emollient have shown reductions of 50%, we assume a more conservative 30% reduction to 16.8%. Using a test of two proportions, a total of 982 babies (491 per arm) are required to detect this difference. Allowing for an approximate 20%

¹ The screening questionnaire includes the question "Has at least one of your baby's blood-related PARENTS, BROTHERS OR SISTERS ever been diagnosed with asthma, eczema (atopic dermatitis) or hay fever (seasonal allergies)?" Strata are split at "Yes" responses vs. "No, or don't know."

loss to follow-up, we plan to enroll 1,250 babies (625 per arm). Sample size calculations were performed using Stata/IC version 16.1.

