2.4. Statistical Testing Framework

All statistical tests will be conducted as two-sided tests of inequality. For example, as our primary analysis, we will test the hypothesis that the ratio of the intervention:control proportions, a relative risk (RR) measure, is significantly smaller than 1 with a two-sided test: **RR \neq 1 vs RR = 1**.

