5.1. Statistical Hypotheses and Outcome Definitions

1. Our primary hypothesis is that the intervention will result in significantly **lower cumulative incidence of provider-diagnosed AD by age 24 months**.

After two years of follow-up, we will calculate the proportions of children diagnosed with AD by trained primary care providers in the intervention and control arms. Clinicians will be trained in pediatric AD standard diagnosis criteria.⁴ As our primary analysis, we will test the hypothesis that the ratio of the intervention:control proportions, a relative risk (RR) measure, is significantly smaller than 1 with a two-sided test: **RR ≠ 1 vs RR= 1**. This analysis will be conducted in an intention-to-treat (ITT) analysis dataset of all randomized participants with multiple imputation for missing outcomes.

Provider-diagnosed AD, the current gold standard, will be recorded during chart abstraction and referred to as **GS-AD**. The case report form (CRF) includes a question:

Was there a diagnosis of AD (includes eczema, atopic eczema, atopic dermatitis, and neurodermatitis)? with forced choice responses:

- 1, Yes
- 0, No / No documentation
- 2, Not sure / Possible - AD diagnosis is not confirmed

The CRF further elaborates:

To check "Yes", there must be an official diagnosis from a provider. If a provider is considering eczema as a possibility, or if a parent thinks the child has eczema, mark "Not Sure/Possible" and provide verbatim description from the medical record. Choose "Not sure/Possible" if there is some evidence of eczema but no official diagnosis.

All "not sure/possible" records and their explanatory notes will be reviewed by the principal investigator or dermatology physician co-investigators under blinding before the dataset is locked for analysis. Fields describing the presence and date of onset of similar or comorbid conditions-- such as candida of the skin, impetigo, and molluscum--are part of this record. Parent responses to the Childhood Eczema Questionnaire^{5,6} (CEQ) (see item 2c below) will also be available for review during this determination.

After this review, any child with a "Yes" response or adjudicated as probable AD by physician reviewers will be considered to have AD and the outcome variable will be set to equal 1. "No" and "Not sure" responses adjudicated as not probable AD will be considered not AD and the outcome will be set to 0.

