Over the last week, how much has your child having eczema been a problem at BATH TIME?

3, Very much | 2, A lot | 1, A little | 0, Not at all

10. Delayed onset of AD, with age of onset determined by

a) provider-recorded date of first diagnosis retrieved from record review of chart by research coordinator

[Field:] Date (or age of child in months) of first AD diagnosis in the chart

b) parental report of eczema age of onset to the nearest 3 months (based on quarterly contacts)

Note: For interval-censored analysis, these variables will use the date of visit/response and previous visit/response as the end and start of the interval, respectively.

11. Lower mean days of disrupted sleep in the past week for infants reported by parents at 12 and 24 months, taken from the single item (#4) in the IDQoL.

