5.9. Missing Data

The approach to missing data will be guided by sources such as Jakobsen et al²¹ on missing data in randomized trials.

Definition of missingness in the primary outcome: The primary outcome, AD by 24 months of age, will be ascertained through review of medical records by research personnel blinded to intervention status and will be considered *not missing* if either (1) a diagnosis of AD is found for any visit before age 24 months (± 3 months), *or* (2) no diagnosis is found *and* the child had at least one visit in the 24-month window. The outcome will be considered missing if those conditions are not met, i.e. we

find no diagnosed AD before age 2 years *and* no clinic visit within ± 3 months of the child's second birthday.

COVID-19 pandemic as a cause of missingness: Because the primary outcome depends on an in-person clinic visit, it is likely to be missing for children who would otherwise have had visits during periods when the clinic was not offering in-person care or when parents declined to bring children for non-urgent care. The study team discussed extending the window for chart reviews to mitigate this effect, but this would require contacting parents for consent and was not adopted.

Missingness in other variables: Other variables from parent report will be considered missing if the response is absent or "don't know/unsure" or similar. In chart reviews, missingness will occur if a visit is not found, but if a visit is found, a "not found" for a particular category (e.g. medication) will be considered a non-missing "no." Validated multi-item scales will be scored according to published guidelines when available. When guidelines are not available, decisions about how to treat missing responses will be made and recorded before the dataset is locked for analysis.

If $\leq 5\%$ of observations are missing the primary outcome, then multiple imputation methods will not be of benefit and we will perform analysis without imputation. The treatment assignment, family history of atopic dermatitis, and recruiting clinic are assigned or used to create arm assignments and so will be complete for all participants.

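### AD charted before randomisation but not reported by the parent is scored as an incident event, and no rule uses the diagnosis date to separate it

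*Protocol*

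**What the plan says.** **Outcome.** Protocol 2.2.1 states: "Any diagnosis of AD made by the trained provider during the first 27 months of life will be considered as having developed AD". Protocol 6.3 has the abstractor count a diagnosis from whichever visit it appears at, and Protocol 10.2.1 gives only the upper limit of 27 months. SAP 5.1 sets the outcome to 1 for a child with a yes entry or one "adjudicated as probable AD by physician reviewers will be considered to have AD", with no date condition. SAP 5.9 treats the outcome as observed when "a diagnosis of AD is found for any visit before age 24 months", give or take three months. None of these sections mentions randomisation.

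**Eligibility.** Protocol 4.3 excludes a dyad when "Infant has established eczema as diagnosed by the primary healthcare provider at clinic site of enrollment per parent report". SAP 4.1 shows that this is one screening question put to the parent. Protocol 6.1 has form logic confirm eligibility, with optional review by data coordinating centre staff. No baseline skin examination or chart check is described. Enrolment is open until day 63 (Protocol 4.4.1).

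**Analysis set and dates.** SAP 3.6 keeps every randomised infant in the ITT population. Protocol 4.7.1 lets an investigator end participation when an exclusion criterion comes to light later, but this neither recodes the outcome nor removes the infant from ITT. The chart form has the field "Date (or age of child in months) of first AD diagnosis in the chart" (SAP 5.1, item 10), used for age of onset. None of the sensitivity analyses in SAP 5.10 sets aside diagnoses that predate randomisation.

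**The concern.** The primary objective is to lower the cumulative incidence of AD, which presupposes infants who are free of AD when follow-up starts. Eligibility is settled by what the parent reports, while the outcome is settled by what the chart holds from birth onward. The two sources can disagree over the first nine weeks.

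There are two ways for a pre-randomisation chart entry to pass screening:

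- The parent does not recall a diagnosis, or was never told of it.
- The entry was tentative. The exclusion needs established, diagnosed eczema, whereas the outcome also accepts qualified entries (Protocol 6.3) and uncertain ones later judged probable (SAP 5.1). A parent can answer the screener truthfully and the infant can still be scored as a case.

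An emollient mailed after enrolment cannot affect such an event, so it contributes a relative risk of 1 to a comparison designed around 0.70. The same infants enter the 12- and 18-month incidence and time-to-onset analyses. The design has little reserve: 625 per arm less 20% leaves 500 evaluable, against 491 required.

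**Working it through.** **Inputs.** SAP 2.3: control risk 24%, intervention risk 16.8% (RR 0.70), 1:1 allocation, 491 per arm, sized to "provide an overall type I error rate of 0.05 and 80% power". SAP 2.4: "All statistical tests will be conducted as two-sided tests of inequality". The share q of randomised infants with AD charted before randomisation but unreported is **not in the documents**; it is varied here from 0.5% to 3%.

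**The plan's own figure.** Two-proportion test, pooled variance under the null, no continuity correction, with p̄ = (0.24 + 0.168)/2 = 0.204:

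n per arm = [1.960·√(2·0.204·0.796) + 0.842·√(0.24·0.76 + 0.168·0.832)]² / 0.072² = (1.117 + 0.478)² / 0.005184 ≈ 490.5, rounded up to 491.

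This matches the SAP, and power at 491 per arm is 80.0%.

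**Dilution.** Prevalent infants count as events in both arms with no treatment effect; the RR is 0.70 in the rest. SAP 2.3 does not say whether 24% includes prevalent AD, so both readings are shown.

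- Reading A, 24% is total control risk: control = 0.24; intervention = q + 0.7(0.24 − q).
- Reading B, 24% is the risk among AD-free infants: control = q + 0.24(1 − q); intervention = q + 0.168(1 − q).

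Example at q = 2%. A: 0.02 + 0.7·0.22 = 0.174, and 0.174/0.24 = 0.725. B: 0.1846/0.2552 = 0.7235.

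| q (assumed) | RR, A | Power, A | RR, B | Power, B |
|---|---|---|---|---|
| 0 | 0.700 | 80.0% | 0.700 | 80.0% |
| 0.5% | 0.706 | 78.2% | 0.706 | 79.1% |
| 1% | 0.7125 | 76.4% | 0.712 | 78.1% |
| 2% | 0.725 | 72.4% | 0.7235 | 76.2% |
| 3% | 0.7375 | 68.1% | 0.734 | 74.2% |

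**After setting these infants aside.** The RR returns to 0.70 with 491(1 − q) per arm. Control risk is (0.24 − q)/(1 − q) under A and 0.24 under B.

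| q (assumed) | Power after removal, A | Power after removal, B |
|---|---|---|
| 0.5% | 79.0% | 79.8% |
| 1% | 78.0% | 79.6% |
| 2% | 75.8% | 79.2% |
| 3% | 73.5% | 78.8% |

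Under A only part of the power comes back, because fewer incident events remain. At q = 1% the loss is 3.6 points (80.0 − 76.4) and removal recovers 1.6 (78.0 − 76.4). Under B removal recovers nearly all of it.

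**The case against.** The strongest reply is that q is probably small. It covers only AD that was charted by day 63 and that the parent did not report, when asked directly about a diagnosis made at most nine weeks before. Clinics encourage enrolment before one month of age (Protocol 4.4.1). The diagnostic criteria in Protocol Table 1 require itch and a chronic or relapsing history, which are hard to establish so early. A q of 3% would mean that 3/24 = 12.5% of all control-arm AD under reading A was already charted and unreported. This stands as a limit on size, although the acceptance of qualified chart entries weakens the protection that the criteria give. The gap in the outcome definition remains.

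It is also fair to say that charted AD by 27 months among all randomised infants is a legitimate pragmatic endpoint. It is; the difficulty is that the plan describes it as incidence and gives no means of seeing how much is prevalent.

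A reader might infer that same-visit diagnoses should be removed too, since "The typical structure will place a tablet computer in the waiting room, recruitment kiosk or exam room to initiate study procedures" (Protocol 4.6) and the clinician may chart AD minutes later. The documents do not support this. Consent and the enrolment questionnaire come first and may be finished at home (Protocol 4.4.1, 4.4.4). Arm notification goes out on randomisation (4.4.5) and parents may disclose it (4.5). A same-day diagnosis can therefore follow allocation and be influenced by it, and a date field cannot order the two. Removing those infants could be a post-randomisation exclusion.

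**Conclusion.** The gap holds on the text: AD charted before randomisation and not reported by the parent is scored as an incident event. The consequence is a balanced dilution, with the RR moving toward 1 for any q above zero and a power loss of about 2 (reading B) to 4 (reading A) points for each 1% of prevalent infants. The figures assume the plan's 24% and RR 0.70, 491 analysed per arm, no effect of emollient on prevalent cases, and a q that the documents do not supply. At 0.5% the effect is minor.

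A reader might go further and infer a biased test or a seriously underpowered trial. Neither follows. Randomisation balances these infants, so type I error is unaffected, and the larger power losses need values of q for which the documents offer no evidence. Nor do the documents show that early events weigh more in the time-to-onset analysis: SAP 5.4 specifies pooled logistic or interval-censored methods indexed to quarters, with no early weighting.

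This is a low-cost improvement worth making before the data are locked. Without a count of these infants, nobody can say afterwards whether dilution mattered.

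**What to change.** In Protocol 2.2.1 and 6.3 and SAP 5.1 and 5.9, state that a charted AD diagnosis, including an entry later adjudicated as probable, is prevalent and not an incident event when it is dated **strictly before** the randomisation date. Then:

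- Blinded abstractors flag these infants from the dated entry, in the same way in both arms.
- Flagged infants are set aside from the at-risk set for the AD incidence analyses (primary, 12 and 18 months) and the time-to-onset analyses. The rule uses a fact fixed before allocation, so it preserves the randomised comparison.
- The number set aside is reported per arm, and the all-randomised result is shown alongside.
- Same-day diagnoses stay in the main analysis and are set aside only in a sensitivity analysis.

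Cost: mainly wording, using a date field already on the chart form. That field also accepts age in months, which is too coarse here, so charts with only an age for a diagnosis before about 3 months need the calendar date retrieved. Chart audits were under way when SAP version 3.0 was written, so some re-abstraction may be needed. A few randomised infants leave the denominator, which the all-randomised result covers. The rule cannot detect AD that was present but uncharted at randomisation.
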